HI4T trial

Prospective, parallel-group, open-label randomized
controlled trial of four treatment regimens for trichuriasis
in pediatric patients

NCT04041453

Protocol version 1.0

29NOV2018

HI4T Trial - PROTOCOL SYNOPSIS

STUDY IDENTIFICATION	Prospective, parallel-group, open-label randomized controlled trial of four treatment regimens for trichuriasis in pediatric patients. HI4T trial.
TYPE AND DEVELOPMENT CLINICAL PHASE	Phase II non-inferiority randomized clinical trial
SPONSOR	Fundacion Mundo Sano, Spain
INVESTIGATOR	[name], Principal Investigator [name], PhD. General Coordination
STUDY CENTERS	
 • Universidad Autonoma de Honduras Laboratory centers: 
 • Genetics Research Center. UNAH, Tegucigalpa, Honduras • [name] lab. CIVETAN, UNCPBA - Tandil, Argentina (pk). • [name] lab, IIET, UNSa – Orán, Argentina (resistance)
ETHICAL COMMITTEE APPROVAL	CEI-MEIZ, UNAH, HON & Brock University, Canada.
OBJECTIVES	
Primary endpoints Cure rate (CR) (conversion from being egg positive pre-treatment to egg negative post-treatment) for Trichuris infection will be assessed using the quadruple Kato-Katz method at 14 to 21 days post-treatment.
 
Secondary endpoints
 
 • To evaluate the safety and tolerability of the interventions. • To measure the egg reduction rate of the different treatment arms against T. trichiura. • To validate the multi-parallel qPCR for the determination of efficacy outcomes. • To determine the presence of isolates with resistance to the study drugs in the pre and post treatment isolates. • To determine population pk parameters of IVM through a population pk approach.
DESIGN AND METHODOLOGY	Phase II, open label randomized, controlled, parallel groups clinical trial in patients infected with T. trichiura .

TREATMENT ARMS	
 • Group 1: single dose of ALB 400 mg. (active control arm). N:39 • Group 2: single dose ALB 400mg + IVM 600µg/Kg. N: 57 • Group 3: daily dose ALB 400mg for 3 consecutive days. N:24 • Group 4: daily dose ALB 400mg + IVM 600µg for 3 consecutive days. N:57 
Total Study Population: 177

INCLUSION AND EXCLUSION CRITERIA	
Inclusion Criteria The study population will consist of participants who meet the following selection criteria:
 
 1. Individuals of both sexes infected with T. trichiura. 2. Weight ≥15 kg. 3. Age: 2 to 14 years old. 4. Free acceptance to participate in the study by obtaining signed informed consent form approved by the EC. 
Exclusion Criteria Participants meeting the following criteria cannot be selected:
 
 1. Intake ALB, mebendazole and/or IVM within the previous 3 months. 2. Background of allergy, idiosyncrasy or hypersensitivity to drugs or its excipients. 3. Acute clinical conditions (including diarrhea). 4. Participation in another clinical trial during the 3 months preceding the drug administration. 5. Pregnancy.
SAMPLES COLLECTION	
Fresh stool sample in a 60ml plastic container at screening. One sample 14 to 21 days post treatment

ANALYTICAL METHODS	
Efficacy outcomes:
 
 • Single Kato Katz. • Multiparallel qPCR 
Safety: frequency, distribution and severity of AEs and SAEs. Resistance: molecular biology PK: HPLC

Study medication	
Albendazole: Nematel, ELEA Argentina. 400mg tabs Ivermectin: IVER P, ELEA Argentina. 6mg tablets

Introduction - Justification

Infection with *T. trichiura* is highly prevalent in Honduras and principally affects pediatric populations leading to growth and development impairment.

Various medications have been approved for the treatment of *T. trichiura* infection, including albendazole (ALB) and mebendazole (MBZ), both belonging to the benzimidazole family (BZ). These treatments (especially ALB) are used in Honduras during mass-drug administration campaigns.

Currently, the recommended treatment regimen is a single-dose of 400 mg of albendazole (ALB); however, the efficacy of this drug is considerably limited against *T. trichiura* infection (17%, CI of 95% 8 – 31%). This limited efficacy has raised concerns due to an increase in the

proportion of patients with this infection in areas where treatment is regularly administered. Several explanations for this limited efficacy have been explored, including lack of treatment compliance, the amount of time the parasite is exposed to the drug in the intestine, and more recently, the emergence of parasitic resistance to ALB.

Due to ALB low efficacy as well as its limited spectrum, other countries have started using ivermectin (IVM) for the treatment of helminths. Trials using ivermectin have demonstrated its high tolerability and safety. Studies involving adults using high dosages of ivermectin showed good safety profile (doses of up to 10 times (10x) the 200µg/kg).

Higher IVM doses didn't result in differences of adverse events in comparison with a placebo. Ivermectin has also been utilized for treating *Pediculosis capitis* in pediatric populations. The approved dose of 400 µg/kg in these clinical trials was well tolerated with only 1.8% of patients (7 of 398) suspending the treatment due to adverse effects (a similar proportion to the group that received 0.5% malathion lotion).

It has been demonstrated, especially in parasitic infections of veterinary importance, that using a single medication to treat parasitic infections can contribute to the emergence of anthelmintic resistance.

The combination of two different drugs is currently considered the best route for avoidance of resistance. This also helps in reaching target levels of prevalence set out by control campaigns.

In accordance with preliminary information, the combination of albendazole/ivermectin (ALB/IVM) could have increased benefits in terms of efficacy without increasing adverse effects.

The present study is proposing the use of a high dose of IVM (600 µg/kg of weight) in children, with the purpose of determining the safety, tolerability and efficacy of this treatment co-administered with albendazole.

The results of this study will help determine if the co-administration of a simplified dose of IVM/ALB is a viable treatment for *T. trichiura* infection among endemic populations.

The study communities of La Hicaca and surrounding villages are located in Honduras. Previous studies performed by our research group in these communities have found a prevalence of >60% in children up to 14 years of age.

Methodology

We propose a prospective clinical trial, with parallel control groups, randomized and incorporating four different treatment regimens (dose-ranging arms), as follows:

- **Arm 1:** Single dose of ALB* 400mg (Active control arm)
- **Arm 2:** Single dose of ALB 400mg + IVM** 600µg/Kg
- **Arm 3:** Daily dose ALB 400mg / 3 consecutive days
- **Arm 4:** Daily dose ALB 400mg + IVM 600µg/kg 3 consecutive days

*ALB (ALBENDAZOL): Nematel® 400mg tablets

****IVM (IVERMECTINA): Iver P® 6mg tablets**

Pair comparisons for efficacy:

- (P1) Arm 1 vs Arm 2 (ALB vs ALB/IVM600)
- (P2) Arm 1 vs Arm 3 (ALB vs ALB x 3)
- (P3) Arm 1 vs Rama 4 (ALB vs ALB/IVM600 x3)
- (P4) Arm 2 vs Arm 4 (ALB x 3 vs ALB/IVM600 x3)

Sample size calculation

Sample Size calculation was based on the following:

$H_{\text{null}} p1 = p2 = p3 = p4$

$H_{\text{Alternative}}: p2 > p1$

$p3 > p1$

$p4 > p1$

$p4 > p2$

$$n = \frac{\left\{ z_{1-\alpha} \sqrt{\bar{p}(1-\bar{p})} - z_{\beta} \sqrt{w_2 p_1 (1-p_1) + w_1 p_2 (1-p_2)} \right\}^2}{w_1 w_2 (p_2 - p_1)^2}$$

ARM	Expected Cure Rate	Lost-to-follow-up	Sample Size	Inflated lost to follow up
ALB	17%	10%	35	39
IVM-ALB	55%	10%	51	57
(IVM-ALB) x3	85%	10%	51	57
ALB x3	60%	10%	21	24
Total				177

With this information, expected efficacy and size of the population, **we have calculated a required sample size of 177 between 2 and 14 years of age children infected with *T. trichiura*.**

Population - Study procedures

A parasitological survey will be conducted including at least 295 children within the community of La Hicaca and surroundings villages to identify infected children.

After attending an informational meeting and obtaining parental consent and children's assent, all participants will be required to provide information for a short enrollment form. They will then undergo clinical physical exam to determine their health status. Anthropometric measurements (height and weight) will also be collected to estimate standard nutritional indications, according to the following international regulations:

- Body Mass Index (BMI): (BMI for ages 5 – 19)
- Height-for-age: (5-19 years of age)
- Weight-for-age: (5-10 years of age)

Stunted growth, low weight and thinness will be determined using the Anthroplus 2007 software (version 1.0.4) and will be defined as being -2 standard deviations (SD) away from the mean height-for-age, weight-for-age and BMI for age, respectively.

As a precaution, girls who report having commenced menarche (first menstrual period), will be requested to provide a urine sample to rule out pregnancy.

Exclusion Criteria:

- Weight less than 15 kg
- Having taken antiparasitic treatment (ALB, MBZ or IVM) in the past 3 months
- History of allergies, idiosyncrasy or hypersensitivity to the medications (IVM and ALB) used in this study.
- Acute clinical conditions (including diarrhea), based on the clinician investigator judgement
- Participation in another clinical trial within the last 3 months prior to administration of the treatment
- Pregnancy

Once participants are enrolled, a stool sample will be requested to obtain baseline information regarding intestinal parasitic infections.

Those participants who are parasitized only by *T. trichiura* will be enrolled in the clinical trial. Prior to the treatment administrations, blood samples will be collected to establish baseline measurements of hepatic enzymes Alanine transaminase (ALT) and aspartate transaminase (AST) and hemoglobin. Following, participants will be randomly divided into the following groups:

- Arm 1: Single dose ALB 400mg (control group)
- Arm 2: Single dose of ALB 400mg + IVM 600µg/kg
- Arm 3: Daily dose of ALB 400mg for 3 consecutive days
- Arm 4: Daily dose of ALB 400mg + IVM 600µg/kg for 3 consecutive days

Four hours after treatment has initiated, a capillary blood sample will be collected via finger puncture (finger prick) from every participant in Arms 2 and 4 to determine the pharmacokinetics of the IVM (plasma concentration at 4, 24, and 72 hours following administration). Once the assigned regimen has been completed, each participant will undergo a clinical evaluation and a measurement of hepatic enzymes to monitor treatment safety (**safety tests**).

Anemia Diagnosis

Hemoglobin concentration will be determined by the HemoCue method (HemoCue AB, Sweden. www.hemocue.com) which requires a capillary blood sample (by finger prick).

Table 1
Haemoglobin levels to diagnose anaemia at sea level (g/l)[±]

Population	Non -Anaemia*	Anaemia*		
		Mild ^a	Moderate	Severe
Children 6 - 59 months of age	110 or higher	100-109	70-99	lower than 70
Children 5 - 11 years of age	115 or higher	110-114	80-109	lower than 80
Children 12 - 14 years of age	120 or higher	110-119	80-109	lower than 80
Non-pregnant women (15 years of age and above)	120 or higher	110-119	80-109	lower than 80
Pregnant women	110 or higher	100-109	70-99	lower than 70
Men (15 years of age and above)	130 or higher	110-129	80-109	lower than 80

[±] Adapted from references 5 and 6

* Haemoglobin in grams per litre

^a "Mild" is a misnomer: iron deficiency is already advanced by the time anaemia is detected. The deficiency has consequences even when no anaemia is clinically apparent.

Hepatic Enzymes (Transaminases) (Safety Test)

Alanine transaminase (ALT) and aspartate transaminase (AST) levels will be determined by a private clinical laboratory, which will receive the anonymized samples (bearing only the participant identification code). The reference values will be determined by the laboratory but the most common ones are of the following ranges:

ALT = 0 – 40 U/L

AST = 0 – 40 U/L

Should there be any participant with altered hepatic enzymes, they will be examined clinically and undergo another test at the end of the study.

Establishing Parasitic Infection

Stool samples from study participants will be collected and kept refrigerated in coolers. Same day analysis will be done via the Kato-Katz method, following WHO recommendations. A total egg count for each helminthic species will be done and expressed as the number of eggs per gram (EPG) of stool. Based on the EPG, an intensity of infection will be determined, including the categories light, moderate or heavy. Aliquots of each sample using each 95% ethanol and 10% formalin will be preserved for molecular analysis and diagnosis of protozoan infection, respectively.

Treatment Efficacy

To determine treatment efficacy, a method determining “cure rate” (CR) will be used. Cure rate is defined the percentage of subjects who no longer pass eggs after treatment (with a 0-egg count per gram of stool at the end of the treatment period). The formula is as follows:

$$CR = 100\% \times \left(1 - \frac{\text{number of subjects excreting eggs at follow-up}}{\text{number of subjects excreting eggs at baseline}} \right)$$

Comparison of Kato Katz vs multi-panel qPCR for evaluating treatment efficacy

A quantitative qPCR analysis will be done for the determination of intensity of infection in the stool samples provided by the participants, with the purpose being to compare these results with those of the Kato Katz technique. The agreement between both methods will be estimated using the Kappa statistic, which sets out to measure level of agreement between techniques. Values of $\kappa = 0, 0.01-0.20, 0.21-0.4, 0.41-0.60, 0.61-0.80, 0.81-1$ are interpreted as poor agreement, light agreement, moderate agreement, considerable agreement and excellent agreement, respectively.

Identification of genetic mutations associated with BZ resistances before and after treatment

DNA from *T. trichiura* will be extracted from the eggs found in stool samples provided by participants. This DNA will then be analyzed via the qPCR technique, using specific primers for the detection of single-nucleotide polymorphisms (SNPs) associated with resistance to benzimidazoles. The results will be presented using descriptive statistics.

The research participants will be involved in the following procedures:

1. Attend informational meeting where they will receive an invitation letter (Appendix 1) (duration: 30 min)
2. Provide with informed consent: Parents or legal guardians will sign the informed consent (Appendix 2) and children older than 9 years will provide assent (Appendix 3)
3. Fill the enrollment form (10 min) (Appendix 4)
4. Clinical history form and physical examination (15 min) (Appendix 5)
5. Anthropometric measurements (5 min) (Appendix 6)
6. Venipuncture (3 min) (protocol can be found here: <https://brocku.ca/research-at-brock/wp-content/uploads/sites/73/REB-Guideline-Phlebotomy.pdf>)
7. Finger prick (5 min) (protocol can be found here: <https://brocku.ca/research-at-brock/wp-content/uploads/sites/73/SOP02-Finger-Prick-Blood-Sampling-edit.pdf>)
8. Provide fecal samples before receiving treatment and again at 14-21 days after receiving treatment (Appendix 7).

Summary of participation

	Pre-enrollment	Enrollment	Baseline	Day 2	Day 3	Day 14-21
Day	- 30 to -2	-7 to -1	0	1	2	14-23
Stool sample	X					X
Eligibility to RTC		X				
Consent/Assent	X					
Clinical evaluation Safety		X	X	X	X	X
Anthropometry		X				
Randomization			X			
Treatment*			X	X ^b	X ^b	
Sample for PK*			X		X ^b	
Safety tests (Liver enzymes)			X		X ^b	X ^c
Urine pregnancy test		X ^d				

- a. Applicable only to Arms with one-day treatment
- b. Applicable only to Arms with 3-day treatment
- c. Applicable only to research participants with abnormal liver enzymes in previous visits
- d. Applicable only to female participants that experienced menstruation already

Adverse effects

Treatment used in the study

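### Baseline egg count is recorded for every child but has no stated role in the cure-rate comparisons, so precision may be forgone

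*Combined protocol and SAP*

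**What the plan says.** Under Population - Study procedures, a pre-treatment stool sample is planned for everyone enrolled: "Once participants are enrolled, a stool sample will be requested to obtain baseline information regarding intestinal parasitic infections". The Summary of participation table also places the first stool sample before treatment. Under Establishing Parasitic Infection, "A total egg count for each helminthic species will be done and expressed as the number of eggs per gram (EPG) of stool", and then "Based on the EPG, an intensity of infection will be determined, including the categories light, moderate or heavy".

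The primary endpoint in the synopsis is binary: "conversion from being egg positive pre-treatment to egg negative post-treatment". Under Treatment Efficacy, "To determine treatment efficacy, a method determining “cure rate” (CR) will be used", and "Cure rate is defined the percentage of subjects who no longer pass eggs after treatment". The formula given there is a crude proportion with no covariate. Four pairs are listed under "Pair comparisons for efficacy": P1 is Arm 1 vs 2, P2 is Arm 1 vs 3, P3 is Arm 1 vs 4 and P4 is Arm 2 vs 4. They are sized under Sample size calculation with a two-proportion formula.

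On allocation, the text says only that "participants will be randomly divided into the following groups". No stratification factor appears. No significance test, regression model, alpha, power or multiplicity rule is stated for the cure-rate comparisons.

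Baseline egg counts do have other uses. They define who is infected, and so the cure-rate denominator. They are also implied by the secondary egg reduction rate.

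**The concern.** Cure means reaching a zero egg count, so the starting egg count is the baseline value of the quantity that defines the outcome. It is the natural covariate and will already be in the database. If it predicts cure, a comparison that ignores it has a larger standard error than necessary.

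This matters more here because the arms are small and, at the inferred design values, P2 and P4 have only about 80% power. With no stratification, chance differences in baseline intensity are also likely to be visible. For 35 vs 21 children the standard error of the difference in mean log EPG, in SD units, is √(1/35 + 1/21) = 0.276. Assuming normality, the chance of a gap above 0.3 SD is about 28%. For 51 vs 51 it is about 13%.

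The choice also needs to be made in advance. A decision to adjust that is taken after unblinded results are seen would be open to challenge.

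**Working it through.** **1. Reproducing the plan's sample size.** From the sample-size table, the expected cure rates are 17% (ALB), 55% (IVM-ALB), 85% (IVM-ALB x3) and 60% (ALB x3). The evaluable numbers are 35, 51, 51 and 21, with 10% loss to follow-up. Alpha and power are not stated. I tried 0.05/4 = 0.0125 two-sided (z = 2.498) and 80% power (z = 0.842) in the plan's formula, where the total for a pair is

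N = {2.498·√[p̄(1−p̄)] + 0.842·√[w₂p₁(1−p₁) + w₁p₂(1−p₂)]}² / [w₁w₂(p₂−p₁)²]

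- 17% vs 55%, 1:1: (1.199 + 0.371)² / 0.0361 = 68.3, so 34.1 per arm, rounded up to 35.
- 55% vs 85%, 1:1: (1.145 + 0.364)² / 0.0225 = 101.2, so 50.6 per arm, rounded up to 51.
- 17% vs 60%, w₁ = 35/56 = 0.625: (1.176 + 0.379)² / 0.0433 = 55.8, so 34.9 and 20.9, rounded up to 35 and 21.

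Dividing by 0.9 and rounding up gives 39 + 57 + 57 + 24 = 177. The stated figures reproduce exactly. The design therefore assumed no covariate, and 0.0125 two-sided with 80% power is a reasonable inference. One-sided 0.01 with 85% power comes close (35; 51; 36 and 22) but is not exact.

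**2. Effect of adjustment.** Assumptions: logit of cure is linear in standardised log EPG, with the same slope in each arm, and the arm-level cure rates are held at the plan's values. The odds ratio (OR) for cure per SD lower log EPG is varied from 1 to 3, because the documents give no value. With mⱼ(x) the cure probability in arm j at covariate value x:

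- Crude variance: V₀ = p₁(1−p₁)/n₁ + p₂(1−p₂)/n₂
- Adjusted variance: V₁ = E[m₁(1−m₁)]/n₁ + E[m₂(1−m₂)]/n₂ + Var(m₂−m₁)/(n₁+n₂)
- Power: Φ{[|p₂−p₁| − 2.498·SE under the null] / SE under the alternative}, with each n divided by V₁/V₀

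Worked case, P4 at OR 2:

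- V₀ = (0.2475 + 0.1275)/51 = 0.007353.
- V₁ = (0.2234 + 0.1199)/51 + 0.0057/102 = 0.006787, a ratio of 0.923.
- Crude power: (0.30 − 2.498 × 0.0907)/0.0857 = 0.855, so 80.4%.
- Adjusted, with effective n = 51/0.923 = 55.3 per arm: (0.30 − 2.498 × 0.0872)/0.0824 = 0.998, so 84.1%.

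| Pair (evaluable n) | OR 1 | OR 1.25 | OR 1.5 | OR 2 | OR 3 |
|---|---|---|---|---|---|
| P1, 17% vs 55% (35, 51) | 88.3% | 88.6% | 89.4% | 91.1% | 93.9% |
| P2, 17% vs 60% (35, 21) | 80.2% | 80.7% | 81.7% | 84.1% | 88.0% |
| P3, 17% vs 85% (35, 51) | about 100% | about 100% | about 100% | about 100% | about 100% |
| P4, 55% vs 85% (51, 51) | 80.4% | 80.8% | 81.8% | 84.1% | 88.0% |

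The OR 1 column is also the crude power. P4 is taken as Arm 2 vs Arm 4, which the arm numbers and the hypothesis p4 > p2 support. Its bracketed label describes Arm 3 and should be reconciled.

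**3. Simulation check of power.** With 4,000 runs per cell and a likelihood-ratio test, power from crude to adjusted was 80% to 85% (P2) and 81% to 85% (P4) at OR 2. At OR 3 it was 80% to 89% and 83% to 90%. At OR 1 it did not change materially. The direction and size agree with the table.

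**4. Simulation check of false rejection (nominal 1.25%).** Ranges are over several simulations of 3,000 to 4,000 runs per cell. For P2, with 17% cure in both arms:

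- large-sample test of the standardised difference: 2.2% to 3.0%
- adjusted likelihood-ratio test: 1.4% to 2.2%
- crude likelihood-ratio test: 1.2% to 1.9%
- crude pooled z-test: 0.6% to 1.25%

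The reason is sparse data: 0.17 × 56 is only about 10 cures. For P4 the standardised-difference test rejected 1.0% to 1.7% of the time, close to nominal.

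**The case against.** A reader might infer that the plan has chosen an unadjusted analysis and is throwing precision away. The documents do not support that. The cure-rate formula defines a summary, and an unadjusted sample-size formula does not bind the analysis. The plan is silent on the test, so the missing covariate is part of a wider gap: no primary analysis is specified. That part of the objection stands. It does not remove the point, because the missing paragraph has to be written and baseline EPG is a concrete choice to put in it.

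A reader might also infer that adjustment is free: nothing lost if EPG is not prognostic, and power gained if it is. The power half is about right. The error-rate half is not shown for P2, where large-sample adjusted tests reject too often, so part of the apparent gain there is inflated error. This stands and shapes the fix.

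The gain also rests on an assumed prognostic strength. Measurement noise could dilute it, and that noise is unknown because the synopsis gives both quadruple and single Kato-Katz. This too stands.

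Finally, randomisation keeps the crude comparison unbiased, and its standard error already allows for chance imbalance. That is correct. The argument for adjustment is precision, not bias.

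**Conclusion.** The point holds in a limited form. Baseline EPG is collected on every child, and the documents give it no role in randomisation or in the cure-rate comparisons. Precision may be forgone.

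For an assumed OR of 1 to 3 per SD lower log EPG, the gain is 0 to about 8 power points for P2 and P4 (88.0 − 80.2 = 7.8 and 88.0 − 80.4 = 7.6). It is 0 to about 6 for P1 (93.9 − 88.3 = 5.6) and nil for P3. At a modest OR of 1.5 it is only about 1.5 points for P2 and P4.

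These sizes rest on the inferred 0.0125 two-sided level, the planned cure rates, a common slope across arms and the evaluable numbers in the sample-size table. For P2 they also require an inference method that holds its error rate. This is a worthwhile improvement to an analysis not yet written. It is not a flaw that would invalidate the trial.

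**What to change.** Add a short primary-analysis paragraph, fixed before outcome data are examined:

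- For each listed pair, fit a logistic regression of cure on arm with log10 baseline EPG as a continuous covariate.
- Report the result as a standardised (marginal) cure-rate difference, and name that as the estimand, because the conditional odds ratio answers a different question.
- Use permutation or other small-sample inference, at least for P2 (35 vs 21 evaluable).
- State alpha, sidedness and the multiplicity rule, and match the confidence level to them: 98.75% intervals if 0.0125 two-sided per comparison is intended.
- Keep the crude cure rates and the unadjusted comparison as supporting results.
- Reconcile the quadruple and single Kato-Katz statements in the synopsis, so that the precision of the covariate is known.

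The cost is a paragraph of text and slightly more analysis work. No new data, visits or children are needed, and the total of 177 does not change.

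### Kappa against Kato-Katz, the only analysis given for qPCR, cannot by itself meet the objective of validating qPCR for efficacy outcomes

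*Combined protocol and SAP*

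**What the plan says.** The synopsis lists among the secondary endpoints: "To validate the multi-parallel qPCR for the determination of efficacy outcomes". Its analytical methods row places multiparallel qPCR beside Kato-Katz under efficacy outcomes.

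The section Comparison of Kato Katz vs multi-panel qPCR for evaluating treatment efficacy says a quantitative qPCR will be run on participants' stools, "with the purpose being to compare these results with those of the Kato Katz technique". It then names one statistic: "The agreement between both methods will be estimated using the Kappa statistic, which sets out to measure level of agreement between techniques". The kappa values "are interpreted as poor agreement, light agreement, moderate agreement, considerable agreement and excellent agreement, respectively". The section gives no qPCR positivity rule, no time point for kappa, no reference standard and no threshold for success.

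The Treatment Efficacy section defines cure from eggs only: "Cure rate is defined the percentage of subjects who no longer pass eggs after treatment". The list headed "Pair comparisons for efficacy" gives P1 to P4 without naming an assay. No qPCR cure rate, discordance table or qPCR comparison between arms is described.

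The comparator is itself unsettled. The primary endpoint "will be assessed using the quadruple Kato-Katz method at 14 to 21 days post-treatment", while the analytical methods row reads "Single Kato Katz". No accuracy figure is given for either assay.

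**The concern.** Validating an assay for efficacy outcomes means asking whether it gives the same cure rates and the same differences between arms. A stool-level kappa answers another question: how often two classifications coincide beyond chance. Every discordant stool counts against agreement, whether qPCR found an infection that Kato-Katz missed or the reverse.

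Two things are at stake. The secondary objective would end with a coefficient that cannot be interpreted without knowing how accurate Kato-Katz is. The Kato-Katz comparisons would also go without a check that planned data could supply. If Kato-Katz misses more infections where residual egg counts are low, its cure rates are overstated by different amounts in different arms.

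**Working it through.** **The plan's own figure.** The table gives expected cure rates 17/55/60/85% in Arms 1/2/3/4 and evaluable numbers 35/51/21/51. The printed formula reproduces these at two-sided alpha 0.0125 (0.05/4) and 80% power, neither of which is stated. P4 (55% vs 85%) gives 50.6, so 51 per arm. P1 (17% vs 55%) gives 34.1, so 35. P2 (17% vs 60%, ratio 21/35) gives 34.9 and 20.9, so 35 and 21. Dividing by 0.90 gives 39, 57, 24 and 57, total 177. No figure is stated for the kappa analysis.

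**Symmetry.** Let a = both positive, b = Kato-Katz positive only, c = qPCR positive only, d = both negative. Then kappa = 2(ad − bc) / [(a+b)(b+d) + (a+c)(c+d)]. Exchanging b and c leaves it unchanged. This needs no assumption about accuracy.

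**Assumptions for the illustration.** The expected cure rates are taken as Kato-Katz results at follow-up. The table is pooled over 158 children and specificity is 1 for both assays. Kato-Katz positives are 35×0.83 + 51×0.45 + 21×0.40 + 51×0.15 = 68.05 (43.1%). True prevalence in an arm = (1 − cure rate)/Kato-Katz sensitivity. The sensitivities are assumed, because the documents give none.

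**Two opposite situations with the same kappa** (kappa = (po − pe)/(1 − pe)):

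- Perfect qPCR, Kato-Katz sensitivity 0.90/0.75/0.75/0.50. Truly infected: 32.28 + 30.60 + 11.20 + 15.30 = 89.38, so Kato-Katz misses 21.33. Cells a = 68.05, b = 0, c = 21.33, d = 68.62. po = 136.67/158 = 0.865; pe = (68.05×89.38 + 89.95×68.62)/158² = 0.491; kappa = 0.374/0.509 = 0.73.
- Perfect Kato-Katz, qPCR missing 30%. Cells a = 47.64, b = 20.42, c = 0, d = 89.95. po = 137.59/158 = 0.871; pe = (68.05×47.64 + 89.95×110.37)/158² = 0.528; kappa = 0.343/0.472 = 0.73.

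Both lie in the protocol's 0.61–0.80 range. The paired difference in cure rate (qPCR minus Kato-Katz) separates them by sign. In Arms 1/2/3/4 it is −9/−15/−13/−15 points in the first case. In the second, qPCR cure is 1 − 0.7×(1 − cure rate), or 41.9/68.5/72.0/89.5%, so the difference is +25/+14/+12/+5 points.

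**Kato-Katz held the same, errors independent:**

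| Kato-Katz sensitivity, Arms 1/2/3/4 | kappa, perfect qPCR | kappa, 70%-sensitive qPCR |
|---|---|---|
| 0.95/0.90/0.90/0.85 | 0.92 | 0.67 |
| 0.95/0.85/0.85/0.70 | 0.87 | 0.63 |
| 0.90/0.75/0.75/0.50 | 0.73 | 0.54 |
| 0.90/0.70/0.70/0.40 | 0.65 | 0.48 |

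**Arm differences in percentage points, same scenarios.** P4 is taken as Arm 2 vs Arm 4, as in the alternative hypothesis.

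| | True cure %, Arms 1/2/3/4 | P1 | P2 | P3 | P4 |
|---|---|---|---|---|---|
| By Kato-Katz | 17/55/60/85 | 38 | 43 | 68 | 30 |
| Scenario 1 | 12.6/50.0/55.6/82.4 | 37.4 | 42.9 | 69.7 | 32.4 |
| Scenario 2 | 12.6/47.1/52.9/78.6 | 34.4 | 40.3 | 65.9 | 31.5 |
| Scenario 3 | 7.8/40.0/46.7/70.0 | 32.2 | 38.9 | 62.2 | 30.0 |
| Scenario 4 | 7.8/35.7/42.9/62.5 | 27.9 | 35.1 | 54.7 | 26.8 |

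**The case against.** The equal kappas come from two different worlds: one has a poor Kato-Katz, the other a perfect one. A reader might infer that kappa generally fails to rank a good qPCR above a poor one. That does not follow. With the same Kato-Katz and independent errors, the perfect qPCR scores higher in all four scenarios. The order can reverse only if both assays tend to miss the same infections. For example, with 43.1% Kato-Katz positive and a uniform Kato-Katz sensitivity of 70%, fully shared misses give 1.000 for a 70%-sensitive qPCR and 0.642 for a perfect one. This objection stands against the general claim. It does not rescue kappa as the sole analysis, because Kato-Katz accuracy is not stated and even the number of smears differs between two places.

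A reader might also infer that a low kappa would be declared a failure of qPCR. The protocol sets no pass mark and names neither assay as the reference, so it does not prescribe that reading.

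Nor do the figures show that Kato-Katz inflates the treatment effects throughout. P4 is unchanged in scenario 3, and P3 and P4 are larger under truth in scenario 1. The differences stay large in every scenario, and no treatment conclusion is shown to change. The low sensitivities in Arm 4 that drive the bigger shifts are assumptions, and quadruple smears would bear on them.

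Finally, the protocol names no between-arm test for Kato-Katz cure either, so part of the gap is plan-wide. The synopsis does list qPCR as an efficacy method. What is missing is the analysis that would use it.

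**Conclusion.** The point holds in a limited form. Kappa's symmetry, and the fact that it estimates neither cure rates nor arm differences, rest on algebra and on the protocol's own text. Kappa alone therefore cannot meet the stated objective.

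The sizes are illustrative and depend on assumed sensitivities and perfect specificity. On those terms, two opposite situations both give 0.73. Across the four scenarios the true difference is 28 to 37 points for P1 (38 by Kato-Katz), 55 to 70 for P3 (68) and 27 to 32 for P4 (30), so the bias varies in both size and direction. The gap affects a secondary objective and a robustness check. It is not evidence that the primary endpoint is wrong. It is worth correcting because the remedy costs little.

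**What to change.** Keep kappa as a descriptive statistic and add the following to the plan:

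1. A qPCR positivity cut-off fixed before the results are seen, follow-up as the time point for the agreement analysis, and a rule for children who are Kato-Katz positive but qPCR negative at baseline.
2. On follow-up stools, the 2x2 table for each arm with both discordant cells, and the paired difference in cure rate (qPCR minus Kato-Katz) with a 95% confidence interval.
3. P1 to P4 repeated with qPCR-defined cure, as a prespecified sensitivity analysis beside the Kato-Katz results.
4. A statement that discordance alone does not show which assay is wrong. A Kato-Katz-negative, qPCR-positive stool is a Kato-Katz miss only if qPCR specificity is taken as 1.

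The single and quadruple Kato-Katz statements should be reconciled at the same time, since they define the comparator.

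The cost is wording, a few tables and some more secondary estimates. Stools are already collected before treatment and at day 14–21, with aliquots kept for molecular analysis, so no new samples or assays are needed.
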